Breach of confidentiality: There is a potential risk of loss of confidentiality. Consistent with the Federal guidelines, all patients and guardians will be informed of the federally mandated reporting laws for child abuse and neglect, verbally and in the written consent form. Therefore, if abuse or neglect is suspected, per institutional and legal standards and requirements, the Department of Human Services may be called if appropriate and indicated. Risks associated with this reporting include embarrassment, legal consequences, and removal of the child from home.

3. Specific Aims and Hypothesis

Specific Aims	Hypothesis

SA1: Evaluate the safety of CIS-telehealth relative to inpatient and OCIC-in-person among children with similar CHRT-SR scores.
	
 Our working hypothesis is that CIS-telehealth is associated with a greater risk of suicidal event relative to inpatient and in-person OCIC. Response is defined by a delay in first recurrence of a suicidal event and a lower number of suicidal events over 90 days and 180 days. Clinical Features: 
 Severity of suicidal ideation at baseline and over 180 days number of suicidal events at baseline only Substance use at baseline and over 180 days. Sociodemographic features: Age, Gender, Gender Identity, Type of insurance (Public, Private or none), Ethnicity, Race, or living with one biological parent, two biological parents, a stepparent, a relative, or other.

SA2: Examine the effectiveness of CIS-telehealth relative to inpatient and in-person OCIC among children with similar CHRT scores.
	
 Our working hypothesis is that CIS-telehealth will be associated with poorer reduction in emotional arousal and perceived stress levels in response to COVID-19 the pandemic relative to CIS-inpatient and CIS-in-person.

SA3: Assess patient and parent treatment satisfaction with CIS-telehealth relative to inpatient and in-person OCIC among children with similar CHRT scores.
	
 Our working hypothesis is that CIS-telehealth is associated with less patient satisfaction than inpatient and in-person OCIC among children with similar CHRT scores.

Exploratory Aim
	

[figure not shown]
Specific Aims	Hypothesis

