9.1. Sample Size Determination

We proposed to recruit approximately 244 eligible cases that will be followed in three treatment arms: telehealth CIS, in-person OCIC, and inpatient. We expect that the sample sizes for the three arms will be *at least* 75, 75, and 70 respectively. These numbers account for an expected 10 % dropout rate; 220 participants are expected to complete study procedures. Prior evidence suggests that the 6-month inpatient readmission rate for adolescents with a prior history of suicidality is approximately 19%.¹⁰⁸ Preliminary data suggest that almost 10% of adolescents who received OCIC treatment following a suicidal event could have recurrent suicidal attempts during the following 6 months after OCIC treatment (preliminary unpublished data from the sites from Dallas and Cincinnati). Therefore, if we assume the hazard ratio (inpatient group vs. OCIC group) will be approximately 2.8 and the readmission rates over 6 months for the two groups will be 19% (for the inpatient group) vs. 10% (for the OCIC group), we will be able to achieve the statistical power at 0.70 given the two-side alpha value = 0.05. We expect numbers for the

Telehealth CIS to be larger than the inpatient group. We will achieve similar power when we compare the Telehealth CIS group with the inpatient group. The power is likely lower than 0.6 when we compare Telehealth CIS with the OCIC group since the effect size (i.e., hazard ratio < 2). The power calculation, based on the assumption that 19% (inpatient group) vs. 10% (Telehealth CIS or OCIC group) will be the averaged recurrence rates for the two arms across the four sites, was performed using the powerSurvEpi package in the software R. For continuous outcomes, we expect that the two-group comparison can achieve the power at 0.84 when the effect size Cohen's d is 0.5 and sample sizes for the first and second group are 75 and 70, respectively. Alternatively, we will achieve the power at 0.76 if we use ANOVA to evaluate whether the continuous outcome differs among the three groups given the effect size $f^2 = 0.2$

For purposes of analysis, the following populations are defined:

Population	Description
Enrolled	All participants who sign the ICF
Observational	All patients will be followed in three treatment arms (telehealth CIS, in-person OCIC, and inpatient)

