increased risk of serious suicide attempts and suicide.⁶¹⁻⁶³ The cultural context of adolescent suicidal behavior and help-seeking is important and differs among races and ethnic groups.¹⁰⁵ For example, in the Hispanic community, families are much less likely to seek mental health professionals in help seeking and prefer to rely on family first.⁶⁴ Ethnic groups and races differ in rates of adolescent suicidal behaviors.^{105, 106} However, the gap has been decreasing between white adolescent suicides and African American suicides due to an increase in male African American deaths by suicide.⁶⁵⁻⁶⁷ Living situation (living with one biological parent, two biological parents, a stepparent, a relative, or other) is an important HTE for adolescents because living with one parent or the presence of a stepparent was correlated with an increased risk of suicidal thoughts and suicide attempts by adolescents.^{68, 69}

The analysis plan:

To test Aim 1, we will use Cox proportional regression model (CPR) to test whether the telehealth only CIS; outpatient, in-person CIS; and in-patient CIS groups have different incidence rates for recurrent episodes within 3 months. We expect that the sample sizes for the three arms will be *at least* 75, 75, and 70 respectively. To evaluate Aims 2 and 3, we will use the generalized linear model (GLM) to evaluate whether telehealth only CIS; outpatient, in-person CIS; and in-patient CIS groups have different levels of changes in emotional arousal (Aim 2) and treatment satisfaction (Aim 3) at 3 months, after adjusting for several covariates (e.g., age, gender, triage “location”). For CPR, we will have power for our pilot study greater than 0.70 assuming a hazard ratio of 2.8 and greater than 0.8 for our GLM analyses assuming $f^2 = 0.1$ and correcting for multiple comparisons.

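### Sections 4.2 and 9.2.3 give one unqualified Cox power above 0.70 for the three-group Aim 1 test, although section 9.1 concedes much less for telehealth versus OCIC and states no specific alternative for that contrast

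*Combined protocol and SAP*

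**What the plan says.** The SA1 hypothesis in section 3 is that "CIS-telehealth is associated with a greater risk of suicidal event relative to inpatient and in-person OCIC", so telehealth versus OCIC is one of its two contrasts.

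Sections 4.2 and 9.2.3 describe a Cox test of all three groups for recurrence within 3 months, then state: "For CPR, we will have power for our pilot study greater than 0.70 assuming a hazard ratio of 2.8". Neither section names a pair of arms.

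Section 9.1 gives the source of that HR: "if we assume the hazard ratio (inpatient group vs. OCIC group) will be approximately 2.8", with six-month rates of 19% and 10% and a stated power of 0.70, "given the two-side alpha value = 0.05". It expects similar power for telehealth versus inpatient. For the third pair it says "The power is likely lower than 0.6 when we compare Telehealth CIS with the OCIC group", because the HR is expected to be below 2. It describes the rates behind the calculation as "19% (inpatient group) vs. 10% (Telehealth CIS or OCIC group) will be the averaged recurrence rates for the two arms". Expected arm sizes for telehealth, OCIC and inpatient are at least "75, 75, and 70 respectively", and "These numbers account for an expected 10 % dropout rate; 220 participants are expected to complete study procedures".

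**The concern.** The caveat stands only in section 9.1. A reader of 4.2 or 9.2.3 sees one favourable figure for the whole Aim 1 test and does not learn that the plan expects less for telehealth versus OCIC. A reader who does reach 9.1 finds a ceiling with no alternative behind it: no HR is chosen, and the same 10% is attached to both arms.

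Telehealth against in-person crisis care is the comparison of modality that this protocol adds. It is a safety comparison in suicidal adolescents. If its power is low and not stated plainly, a non-significant result is easy to over-read.

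**Working it through.** **Inputs.** Section 9.1: two-sided alpha 0.05; 75 telehealth, 75 OCIC and 70 inpatient, already net of dropout; 19% inpatient and 10% OCIC over 6 months; HR about 2.8 for inpatient versus OCIC; HR below 2 for telehealth versus OCIC. Sections 4.2 and 9.2.3: 3-month window. Section 2.2: 27.3% of 286 Dallas OCIC respondents reported a suicidal event within 6 months of discharge.

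**Formulas.** D is the expected number of events.
- Schoenfeld: power = Φ(√(D·a(1−a))·ln HR − 1.96), where a is the share of patients in one arm.
- Freedman: power = Φ(√(kD)·(HR−1)/(k·HR+1) − 1.96), where k is the allocation ratio.

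**Step 1: the plan's own 0.70 (inpatient versus OCIC).** D = 70×0.19 + 75×0.10 = 20.8. At HR 2.8:
- Schoenfeld: Φ(2.346 − 1.96) = 0.65.
- Freedman: Φ(2.195 − 1.96) = 0.59.

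So 0.70 is not reproduced exactly from the stated inputs. It appears only with a changed input, for example arm sizes before dropout (0.70, Schoenfeld) or a one-sided test (0.71, Freedman). Rates of 19% and 10% also imply HR = ln 0.81/ln 0.90 = 2.0, not 2.8. That mismatch is a separate matter and is not pursued here.

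**Step 2: telehealth versus OCIC.** With 75 per arm, a = 0.5 and k = 1. OCIC has rate p. Under proportional hazards telehealth has rate 1−(1−p)^HR, so D = 75p + 75[1−(1−p)^HR]. OCIC is taken as the lower-risk arm, as in SA1.

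Six months, p = 0.10:
- HR 1.5: telehealth rate 0.146, D = 18.5. Both formulas give 0.14.
- HR 2.0: telehealth rate 0.19, D = 21.75. Schoenfeld: Φ(1.616 − 1.96) = 0.37. Freedman: Φ(1.555 − 1.96) = 0.34.
- Power 0.60 needs HR 2.44 and power 0.80 needs HR 2.92 (Schoenfeld). Both lie outside the plan's own range for this pair.

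**Step 3: the window in 4.2 and 9.2.3.** Under constant hazard the 3-month rate is 1−(1−p)^0.5. For p = 0.10 this is 0.051; at HR 2.0 telehealth is then 0.10 and D = 11.35. Schoenfeld: Φ(1.168 − 1.96) = 0.21. Freedman: Φ(1.123 − 1.96) = 0.20.

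**Step 4: the other base rate.** The 10% in section 9.1 is described as recurrent attempts. The primary endpoint in section 2.2 is a composite that also counts hospitalization and emergency evaluation, for which the Dallas figure of 27.3% is closer. Using it as the base is an assumption. At HR 2.0:
- Six months: D = 75×0.273 + 75×0.4715 = 55.8.
- Three months: D = 75×0.1474 + 75×0.273 = 31.5.

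| OCIC 6-month rate | Window | HR | Events | Schoenfeld | Freedman |
|---|---|---|---|---|---|
| 10% | 6 months | 1.5 | 18.5 | 0.14 | 0.14 |
| 10% | 6 months | 2.0 | 21.75 | 0.37 | 0.34 |
| 10% | 3 months | 2.0 | 11.35 | 0.21 | 0.20 |
| 27.3% | 6 months | 1.5 | 49.0 | 0.29 | 0.29 |
| 27.3% | 6 months | 2.0 | 55.8 | 0.74 | 0.70 |
| 27.3% | 3 months | 2.0 | 31.5 | 0.49 | 0.47 |

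**Step 5: the 0.70 sentence applied to this pair.** At HR 2.8 and p = 0.10 the six-month figures are D = 26.7 and power 0.76 (Schoenfeld) or 0.69 (Freedman). In the 3-month window they are D = 14.1 and power 0.49 or 0.43.

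**Step 6: precision.** If both arms are at 10% over six months, D = 15 and the 95% CI around an HR of 1 has limits exp(±1.96×√(4/15)), or 0.36 to 2.75.

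**The case against.** The plan has a fair defence, and four stronger readings should be set aside.

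- *That 4.2 and 9.2.3 claim more than 0.70 for telehealth versus OCIC and contradict 9.1.* A reader might infer this, but the sentence is conditional on HR 2.8 and names no pair. Power above 0.70 at HR 2.8 and below 0.6 at an HR under 2 can both be true, and on the six-month 10% base the Schoenfeld formula gives 0.76 at HR 2.8.
- *That the 0.6 figure is an arithmetic error.* It is a hedged upper bound, and 0.37 satisfies it.
- *That power is only 0.05 because both arms are given 10%.* That number is the type I error when there is no difference. The shared rate shows only that no alternative was specified, and the sentence most naturally lists inputs for each comparison with inpatient.
- *That power cannot exceed 0.37, or that a doubling of risk is undetectable.* This depends on the 10% base and exactly 75 per arm, while the plan says at least 75. At HR 2.0, 81 to 83 per arm gives 0.39 to 0.40 (Schoenfeld), and the 27.3% base gives 0.70 to 0.74 over six months.

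The sponsor can also say that 9.1 already discloses the weakness, that 4.2 and 9.2.3 call this a pilot, that section 9.2 defers detail to a later analysis plan, and that no non-inferiority claim is planned. All of this is correct. Misreading a null result as equal safety is therefore a risk to guard against, not something the plan proposes. What the defence does not answer is that the caveat is missing from the two sections that state the Aim 1 test, and that 9.1 gives neither an HR nor a rate difference for this pair.

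**Conclusion.** The point stands as a reporting defect in the power statements. The 0.70 figure belongs to a contrast with inpatient but is attached, without that limit, to the whole Aim 1 test. For telehealth versus OCIC the plan offers only a loose ceiling and no specific alternative.

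On the plan's 10% six-month rate, a true doubling of hazard would be missed about 63% to 66% of the time over six months (1 − 0.37 to 1 − 0.34). Over the three months that 4.2 and 9.2.3 specify, it would be missed about 79% to 80% of the time. On the 27.3% base the ceiling of 0.6 is not assured either: power at HR 2.0 is 0.70 to 0.74 over six months, and 0.60 is already reached at HR 1.83 (Schoenfeld). The size of the shortfall thus depends on the base rate and the window, and the plan fixes neither for this pair.

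These figures assume 75 analysed per arm, proportional hazards, OCIC as the lower-risk arm, no covariate adjustment and, for three months, constant hazard. If risk is concentrated soon after the crisis, the three-month loss is smaller.

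**What to change.** - **Sections 4.2 and 9.2.3:** limit the sentence on power above 0.70 to the contrast with inpatient for which it was computed, and carry over the caveat from 9.1.
- **Section 9.1:** replace the 0.6 ceiling with power for telehealth versus OCIC at stated HRs, for example 1.5 and 2.0. Name the base rate, the arm sizes and the follow-up window. The window must match that of the Aim 1 test; six-month figures should not be placed beside a three-month test.
- **Reporting:** present telehealth versus OCIC as an HR with its 95% CI, and state that a non-significant result will not be described as equal safety.

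The cost is wording in three sections and a less favourable stated power. No extra patients are needed.

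### Section 9.1 quotes 0.84 pairwise power at an uncorrected 0.05 although 4.2 and 9.2.3 refer to multiplicity correction, and no rule controls error across the primary Cox pairs

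*Combined protocol and SAP*

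**What the plan says.** Section 9.1 gives power for two kinds of pairwise comparison.

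- **Continuous outcomes.** "For continuous outcomes, we expect that the two-group comparison can achieve the power at 0.84". The assumptions behind this are a standardised difference of 0.5 and groups of 75 and 70. No alpha is given. As an alternative, it offers a three-group ANOVA with power 0.76.
- **Primary Cox outcome.** For inpatient versus OCIC, "we will be able to achieve the statistical power at 0.70 given the two-side alpha value = 0.05". This assumes that "the hazard ratio (inpatient group vs. OCIC group) will be approximately 2.8" and that six-month rates are 19% and 10%. Telehealth versus inpatient is said to have similar power, and telehealth versus OCIC probably less than 0.6. No alpha is attached to these two pairs.

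Sections 4.2 and 9.2.3 carry a different summary: Cox power above 0.70 at a hazard ratio of 2.8, and GLM power above 0.8 at f² = 0.1 "and correcting for multiple comparisons". Neither section names the correction method, the number of comparisons or an adjusted alpha. Both describe the Cox and GLM analyses as testing whether the three groups differ. Neither says how pairs are tested afterwards.

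**The concern.** The plan refers to a multiplicity correction in two places, but the only pairwise continuous power it prints appears to ignore one. If pairs are corrected, a reader of 9.1 is told of more power than the study has. If they are not, the chance of at least one false difference between settings exceeds 5%.

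The second branch matters most for Aim 1, which compares the safety of three care settings for suicidal adolescents through the primary endpoint. Section 9.1 considers all three pairs for that endpoint. The Aim 1 hypothesis in section 3 needs two of them, telehealth against each of the other settings. The plan does not say whether any pair is tested only after an overall test, or at what level.

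**Working it through.** **1. Reproduce the 0.84.** Inputs from 9.1: d = 0.5, n = 75 and 70. For a two-sample t test, the noncentrality is 0.5 × √(75 × 70 / 145) = 3.009 on 143 degrees of freedom.

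| Two-sided alpha | Critical t | Power |
|---|---|---|
| 0.05 (uncorrected) | 1.977 | 0.848 |
| 0.05/2 = 0.025 (two telehealth contrasts) | 2.265 | 0.771 |
| 0.05/3 = 0.0167 (three pairs) | 2.422 | 0.721 |

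Only the first row matches 0.84. Bonferroni is an assumption made here to size the effect. Šidák over three pairs gives nearly the same result as Bonferroni over three, 0.723.

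**2. Check the GLM figure.** A three-group test with 2 df, N = 220 and f² = 0.1 has noncentrality 220 × 0.1 = 22. Power is 0.99 at 0.05 and 0.97 at 0.0167. The claim of more than 0.8 after correction therefore stands. It is an overall test at a larger effect, so it says nothing about a single pair at d = 0.5.

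**3. Familywise error without a gate.** All three groups equal, arms of 75, 75 and 70, each pair at 0.05. By simulation, the chance of at least one false rejection is about 12% for three pairs and 9% for the two telehealth pairs. Independent tests would give 1 − 0.95³ = 14.3% and 1 − 0.95² = 9.75%. The values here are lower because the pairs share arms.

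**4. Overall test first, then pairs at 0.05.** Simulated with the same arms. Familywise error under equality of all three groups is 5.0%. Power for a pair at d = 0.5:

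- two arms equal, means (0, 0, 0.5): about 0.82;
- third arm midway, means (0, 0.25, 0.5): about 0.76.

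**5. Cox power.** Schoenfeld's formula: power = Φ(√(D·p(1−p)) × ln HR − z), where D is events and p is the inpatient share. With the post-dropout arms, D = 70 × 0.19 + 75 × 0.10 = 20.8 and p = 70/145, so √(D·p(1−p)) = 2.279.

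- HR 2.8, alpha 0.05: Φ(2.279 × 1.030 − 1.960) = 0.65. At 0.0167 (z = 2.394): 0.48.
- The stated 0.70 is recovered (0.696) only with pre-dropout arms of 78 and 83, where D = 78 × 0.19 + 83 × 0.10 = 23.12.
- Under proportional hazards, 19% versus 10% implies HR = ln(0.81)/ln(0.90) = 2.0. With 70 and 75, power is then 0.35 at 0.05 and 0.21 at 0.0167.

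**The case against.** The strongest reply is that the correction clause belongs to another number. In its sentence it qualifies the GLM figure at f² = 0.1, and that figure holds after correction with room to spare. The 0.84 in 9.1 reproduces, so it contains no arithmetic error. This stands, and it limits the point: the plan does state a corrected GLM power, and the fault is that the pairwise figure in 9.1 is uncorrected and not labelled so.

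A reader might go further and infer that the Cox power of 0.70 also contradicts a planned correction and should read 0.54, which is Φ(0.524 + 1.960 − 2.394). The documents do not support that. Nothing clearly says the Cox pairs are corrected, and "given the two-side alpha value = 0.05" is attached to inpatient versus OCIC alone. The 0.54 also takes as sound a 0.70 that needs pre-dropout numbers and a hazard ratio at odds with the plan's own rates. What remains for Cox is that error control across pairs is not stated.

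It would equally be wrong to read three-pair Bonferroni into the plan. The documents never mention it, and the aims can be read as needing only two contrasts.

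Two further replies have some force. The analyses are already worded as three-group tests, and 9.1 prints a three-group power of 0.76. But 9.1 presents the ANOVA as an alternative and does not make pairwise tests depend on it. The full SAP is deferred to before database lock, but the contents listed for it in 9.2 (participant selection; missing, unused and spurious data) do not include multiplicity. Finally, this is an observational study that calls itself a pilot, so the gap calls for a clarification and does not undermine the design.

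**Conclusion.** The point holds in limited form. The 0.84 is an uncorrected pairwise power in a plan that elsewhere says the GLM analyses are corrected. Under correction it would be 0.72 to 0.77 with Bonferroni, depending on whether three or two comparisons are counted, or about 0.76 to 0.82 with a gated procedure. These figures assume d = 0.5 and the stated arm sizes of 75, 75 and 70. The GLM figure at f² = 0.1 is sound.

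For the primary Cox comparisons the finding is one of omission. The 12% and 9% error rates apply only if the pairs are tested at 0.05 independently of any overall test, a matter the plan leaves open. The Cox power needs recomputing for reasons beyond multiplicity, and no single corrected value can be read off the stated 0.70.

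**What to change.** 1. For the Cox and GLM analyses, state that the overall three-group test (2 df) is done first and that pairs are tested at two-sided 0.05 only if it is significant. With three groups this is a closed procedure and holds familywise error at 5% for each outcome. It builds on the three-group tests already described in 9.2.3.
2. In 9.1, replace 0.84 with the power of that procedure: about 0.82 if two arms are equal and 0.76 if the third lies midway. Otherwise label 0.84 as uncorrected and, if Bonferroni is chosen, give 0.77 for two contrasts or 0.72 for three.
3. Recompute the Cox power under the same error control, using the post-dropout arm sizes and a hazard ratio consistent with 19% versus 10%.
4. In 4.2 and 9.2.3, say which comparisons are corrected and by what method.

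The cost is a few sentences and the restated power figures, with no extra participants and no change to the models. The downside is that pairwise power for continuous outcomes is slightly lower than now quoted.

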4.2. Number of Participants

We proposed to recruit approximately 244 eligible cases that will be placed in 3 treatment arms: inpatient, in-person OCIC and telehealth CIS. We expect to recruit a small proportion of the suicidal adolescent group in the ED or who receive crisis assessment from telehealth or via phone. To test Aim 1, we will use Cox proportional regression model (CPR) to test whether the telehealth only CIS; outpatient, in-person CIS; and in-patient CIS groups have different incidence rates for recurrent episodes within 3 months. We expect that the sample sizes for the three arms will be *at least* 75, 75, and 70 respectively. To test Aims 2 and 3, we will use the generalized linear model (GLM) to evaluate whether telehealth only CIS; outpatient, in-person CIS; and in-patient CIS groups have different levels of changes in emotional arousal (Aim 2) and treatment satisfaction (Aim 3) at 3 months, after adjusting for several covariates (e.g., age, gender, triage “location”). For CPR, we will have power for our pilot study greater than 0.70 assuming a hazard ratio of 2.8 and greater than 0.8 for our GLM analyses assuming $f^2 = 0.1$ and correcting for multiple comparisons.

Recruitment Plan for Prospective Studies

. Estimated number of potentially eligible study participants	500
. Total number of study participants expected to be screened:	300
. Total number of study participants expected to be eligible of those screened:	270
. Target sample size (use same number stated in milestones):	244
. Total number of practices or centers that will enroll participants:	4
. Projected month first participant enrolled (month after project initiation):	2nd Month

• Projected month last participant enrolled (month after project initiation):	10 th Month
• Projected rate of enrollment (anticipated number enrolled per month of enrollment period):	2- 10/month
• Estimated percentage of participant dropout:	10%

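### Section 9.1 pairs ANOVA power of 0.76 with f² = 0.2, but that effect gives power above 0.999 with the stated arms; 0.76 fits f = 0.2 (f² = 0.04)

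*Combined protocol and SAP*

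**What the plan says.** Section 9.1 (Sample Size Determination) expects arms of at least 75, 75 and 70 for telehealth CIS, in-person OCIC and inpatient care. These are already net of 10% dropout: "220 participants are expected to complete study procedures".

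For continuous outcomes it makes two power statements in succession:

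- For two groups, "we expect that the two-group comparison can achieve the power at 0.84" at Cohen's d = 0.5, where "sample sizes for the first and second group are 75 and 70, respectively".
- For three groups, a power of "0.76 if we use ANOVA to evaluate whether the continuous outcome differs among the three groups given the effect size $f^2 = 0.2".

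No alpha is attached to either. The only alpha in the section belongs to the hazard-ratio calculation: "achieve the statistical power at 0.70 given the two-side alpha value = 0.05".

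Sections 4.2 and 9.2.3 carry a third statement for the same three arms, power "greater than 0.8 for our GLM analyses assuming $f^2 = 0.1$ and correcting for multiple comparisons".

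**The concern.** Cohen's f² is the variance between group means divided by the variance within groups. A value of 0.2 means f = √0.2 = 0.447, which is a large effect, and 220 patients should detect it almost with certainty.

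The printed pair also sits badly with the plan's other figures. The two-group test on 145 patients is given 0.84 at d = 0.5, while the three-group test on 220 patients is given less power for an effect about twice as large. Sections 4.2 and 9.2.3 claim more than 0.8 at f² = 0.1, yet 9.1 claims only 0.76 at f² = 0.2.

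At stake is what a reader takes the study to be able to detect on a continuous outcome. As printed, 9.1 says that a difference of about one standard deviation between arms would be missed 24% of the time (1 − 0.76). If f = 0.2 was meant, the printed effect is five times too large on the f² scale (0.2 / 0.04 = 5), and the effect that goes with 0.76 is hidden.

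**Working it through.** **Inputs.** Three groups of 75, 75 and 70, so N = 220; stated power 0.76; stated effect f² = 0.2 (all from 9.1). Alpha 0.05 is carried over from the survival calculation in 9.1 and is an assumption for the ANOVA.

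**Check of conventions on the two-group figure.** Two-sided t-test, d = 0.5, n = 75 and 70, df = 143. Noncentrality = 0.5 × √(75 × 70 / 145) = 3.009. Power = 0.848 against the stated 0.84. The agreement is close enough to show that the arm sizes and alpha are being read as the plan uses them.

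**Three-group ANOVA.** Power = P(F′ > F crit), where F′ is noncentral F with df (2, N − 3) and noncentrality λ = N × f². At N = 220 the 5% critical value of F(2, 217) is 3.037.

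| Effect | λ at N = 220 | Power at N = 210 | N = 220 | N = 225 | N = 244 |
|---|---|---|---|---|---|
| f² = 0.2 (as printed) | 44 | 0.99998 | 0.99999 | 0.99999 | above 0.99999 |
| f² = 0.1 | 22 | 0.988 | 0.991 | 0.992 | 0.995 |
| f = 0.2, so f² = 0.04 | 8.8 | 0.733 | 0.755 | 0.765 | 0.800 |

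The totals are 70 per arm (210), the stated arms (220), 75 per arm (225) and full enrolment (244). The stated figure is not reproduced at f² = 0.2. Solving for power of exactly 0.76 gives f² = 0.0405 (f = 0.201) at N = 220 and f² = 0.0396 (f = 0.199) at N = 225.

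**Could another input explain 0.76 at f² = 0.2?**

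- A stricter alpha: at N = 220 power is still 0.998 at alpha 0.001. Reaching 0.76 needs alpha of about 6 × 10⁻⁸, which no plausible multiplicity correction produces.
- A smaller sample: 0.76 needs about 48 patients in total.
- Reading 0.2 as eta-squared: f² = 0.2 / 0.8 = 0.25, and power is again above 0.999.
- A per-arm n entered as the total (61 to 75): power is 0.87 to 0.93.

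None of these gives 0.76.

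**The effect in standard deviations.** With weights 75/75/70, the largest difference between arms that a given f² implies depends on the pattern of means. The range below runs from one arm differing from the other two to one arm lying midway between them.

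- f² = 0.2: 0.94 to 1.10 SD.
- f² = 0.04: 0.42 to 0.49 SD, in line with the d = 0.5 of the two-group sentence.

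**The statement in 4.2 and 9.2.3.** At f² = 0.1, N = 220 and 2 numerator df, power is 0.991 at alpha 0.05 and 0.973 at 0.05/3. Ten further residual df spent on covariates leave it at 0.973. Power above 0.8 therefore holds with margin when 0.1 is read as f², so the label looks right there and wrong in 9.1.

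**The case against.** The arithmetic is not in dispute. The best case against the point is that it matters little and that the explanation is not exact.

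- **Nothing depends on the sentence.** 9.1 offers it as an alternative calculation. It sets neither the 244 nor the split between arms; the primary outcome is time to event, and Aims 2 and 3 name a generalized linear model. The error also understates power, so it does not oversell the study. All of this stands, and it is why the severity is low.
- **The match is approximate.** At the stated arms, f = 0.2 gives 0.755, which rounds down at four decimals (0.7546) to 0.75; a printed 0.76 needs 75 per arm (0.765). Likewise 0.848 rounds to 0.85, while 70 against 70 gives 0.836, which rounds to the printed 0.84. The authors may have used slightly different arm sizes for the two figures. This stands as a reason to ask rather than assert, but gaps of about 0.01 are nothing beside the gap between 0.76 and 0.99999.
- **The comparison with 4.2 and 9.2.3 is between different analyses.** One is an unadjusted ANOVA, the other a covariate-adjusted model with an unspecified correction, where f² is a partial effect. This is fair: the comparison supports the point but does not prove it. The finding rests on the direct recomputation.
- **The superscript could be a text-extraction fault.** This is unlikely, since the same symbol appears in 4.2 and 9.2.3, where it fits the stated power.

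**Conclusion.** The concern holds: the pair in 9.1 is wrong as written. At f² = 0.2 the three-group ANOVA has power above 0.999 with the stated arms, not 0.76. The only reading tried that comes close to the stated power is f = 0.2 (0.755 at N = 220, 0.765 at N = 225). That this was intended is an inference. The conclusion assumes alpha 0.05 for the ANOVA but does not depend on it, since power at f² = 0.2 is still 0.998 at alpha 0.001. The consequence is a misstated design figure of low severity, with no effect on sample size, analysis or decision rules.

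**What to change.** In 9.1, have the sponsor confirm from the original calculation which effect size was entered, then restate the pair so that its parts agree:

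- most likely f = 0.2 (f² = 0.04), with power about 0.75 to 0.76; or
- if f² = 0.2 was truly meant, power above 0.99.

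State the alpha and the N (or arm sizes) used. The f² = 0.1 statement in 4.2 and 9.2.3 needs no change on this account. The cost is the wording of one sentence.
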